13.2 Laboratory data

The summary of lab data will only include treatment emergent data, which are defined as those lab assessments after the first dose of study treatment and on or before last dose + 84 days.

Reported laboratory assessments with either a less than or greater than sign (“<” or “>”) will be used for analysis after removal of the sign and conversion to standard unit. These laboratory data will be displayed in listings using the standard unit with the reported sign (“<” or “>”).

The summary of laboratory evaluations will be presented for three groups of laboratory tests (hematology, chemistry and urinalysis). In addition to the individual laboratory parameters the ratios “total cholesterol / HDL” and “apolipoprotein B / apolipoprotein A1” will be derived and summarized.

For urinalysis, frequency tables will be presented.

Descriptive summary statistics for the change from baseline to each study visit will be presented. These descriptive summaries will be presented by laboratory test and treatment group. Change from baseline will only be summarized for subjects with both baseline and post baseline values and will be calculated as:

$$\text{change from baseline} = \text{post baseline value} - \text{baseline value}$$

For each parameter, the maximum change (maximum decrease and maximum increase) from baseline, if appropriate for each study phase, will be analyzed analogously.

In addition, shift tables will be provided for all parameters to compare a subject’s baseline laboratory evaluation relative to the visit’s observed value. For the shift tables, the normal laboratory ranges will be used to evaluate whether a particular laboratory test value was normal, low, or high for each visit value relative to whether or not the baseline value was normal, low, or high. If appropriate, the shifts to the most extreme laboratory test value within a treatment phase (either initial or entire) will be presented as well (including category “high and low”). These summaries will be presented by laboratory test and treatment group.

The following laboratory parameters will be analyzed with respect to numerical Common Terminology Criteria for Adverse Events (CTCAE) grades, given in [Table 13-2](#): hemoglobin, platelets, white blood cell count, neutrophils, lymphocytes, creatinine, total bilirubin (TBL), gamma-glutamyl transferase (GGT), alanine aminotransferase (ALT), aspartate aminotransferase (AST), alkaline phosphatase (ALP), glucose, cholesterol, triglycerides (TG).

These summaries will be split into hematology and chemistry for study level reports and the pooled summary of clinical safety.

Table 13-2 CTCAE grades for laboratory parameters to be analyzed

CTCAE v4.0 Term	Grade 1	Grade 2	Grade 3	Grade 4
HGB decreased (Anemia)	<LLN – 100 g/L	<100 – 80 g/L	<80 g/L	
Platelet count decreased	<LLN – 75.0 x10e9 /L	<75.0 - 50.0 x10e9 /L	<50.0 – 25.0 x10e9 /L	<25.0 x 10e9 /L
White blood cell decreased	<LLN - 3.0 x 10e9 /L	<3.0 - 2.0 x 10e9 /L	<2.0 - 1.0 x 10e9 /L	<1.0 x 10e9 /L
Neutrophil count decreased	<LLN - 1.5 x 10e9 /L	<1.5 - 1.0 x 10e9 /L	<1.0 - 0.5 x 10e9 /L	<0.5 x 10e9 /L
Lymphocyte count decreased	<LLN - 0.8 x 10e9/L	<0.8 - 0.5 x 10e9 /L	<0.5 - 0.2 x 10e9 /L	<0.2 x 10e9 /L
Creatinine increased*	>1 - 1.5 x baseline; >ULN - 1.5 x ULN	>1.5 - 3.0 x baseline; >1.5 - 3.0 x ULN	>3.0 baseline; >3.0 - 6.0 x ULN	>6.0 x ULN
TBL increased	>ULN - 1.5 x ULN	>1.5 - 3.0 x ULN	>3.0 - 10.0 x ULN	>10.0 x ULN
GGT increased	>ULN - 2.5 x ULN	>2.5 - 5.0 x ULN	>5.0 - 20.0 x ULN	>20.0 x ULN
ALT increased	>ULN - 3.0 x ULN	>3.0 - 5.0 x ULN	>5.0 - 20.0 x ULN	>20.0 x ULN
AST increased	>ULN - 3.0 x ULN	>3.0 - 5.0 x ULN	>5.0 - 20.0 x ULN	>20.0 x ULN
ALP increased	>ULN - 2.5 x ULN	>2.5 - 5.0 x ULN	>5.0 - 20.0 x ULN	>20.0 x ULN
Glucose increased (Hyperglycemia)	; >ULN - 8.9 mmol/L	>8.9 - 13.9 mmol/L	>13.9 - 27.8 mmol/L	>27.8 mmol/L
Glucose decreased (Hypoglycemia)	<LLN - 3.0 mmol/L	<3.0 - 2.2 mmol/L	<2.2 - 1.7 mmol/L	<1.7 mmol/L
Cholesterol high	>ULN - 7.75 mmol/L	>7.75 - 10.34 mmol/L	>10.34 - 12.92 mmol/L	>12.92 mmol/L
Hypertriglyceridemia	1.71 - 3.42 mmol/L	>3.42 - 5.7mmol/L	>5.7 - 11.4 mmol/L	>11.4 mmol/L

*Note: for "creatinine increased" the baseline criteria do not apply.

Note: Grade 4 Hemoglobin events were defined as fatal anemia.

Shift tables will be presented comparing baseline laboratory result (CTCAE grade) with the worst results (expressed in CTCAE grade) during the treatment phase (either initial or entire) analyzed. Of note, baseline will be defined as last assessment prior to first dosing in initial treatment phase. Subjects with abnormal laboratory values will be listed and values outside the normal ranges will be flagged.

Summaries for newly occurring or worsening clinically notable lipid abnormalities will also be provided cumulatively for each of the following parameters and categories:

- HDL:
 - <=LLN
 - <0.8 x LLN
- LDL, cholesterol, triglycerides:
 - >=ULN
 - >1.5 x ULN
 - >2.5 x ULN

Newly occurring or worsening liver enzyme abnormalities will also be summarized based on the event criteria given in [Table 13-3](#):

Table 13-3 Liver-related events

Parameter	Criterion
ALT	>3xULN; >5xULN; >8xULN; >10xULN, >20xULN
AST	>3xULN; >5xULN; >8xULN >10xULN; >20xULN
ALT or AST	>3xULN; >5xULN; >8xULN >10xULN; >20xULN
TBL	>1.5xULN, >2xULN, >3xULN,
ALP	>2xULN, >3xULN, >5xULN
ALT or AST & TBL	ALT or AST >3xULN & TBL >2xULN; ALT or AST >5xULN & TBL >2xULN; ALT or AST >8xULN & TBL >2xULN; ALT or AST >10xULN & TBL >2xULN
ALP & TBL	ALP >3xULN & TBL >2xULN ALP >5xULN & TBL >2xULN
ALT or AST & TBL & ALP	ALT or AST >3xULN & TBL >2xULN & ALP <2xULN (Hy's Law) Note: elevated ALP may suggest obstruction as a consequence of gall bladder or bile duct disease; ALP may also be increased in malignancy. FDA therefore terms Hy's Law cases as indicators of pure hepatocellular injury . This does not mean that cases of ALT or AST >3xULN & TBL >2xULN & ALP ≥2xULN may not result in severe DILI.

Notes:

In studies which enroll subjects with pre-existing liver disease, baseline LFT may be increased above ULN; in such a case it is meaningful to add the condition "and worse than baseline" to the abnormality criteria

For a combined criterion to be fulfilled, all conditions have to be fulfilled on the same visit. The criteria are not mutually exclusive, e.g. a subject with ALT = 6.42xULN is counted for ALT >3xULN and ALT >5x ULN.

Individual subject data listings will be provided for subjects with abnormal laboratory data. Data of subjects with newly occurring or worsening liver enzyme abnormalities will be listed in an additional listing.

Boxplots over time will be presented for selected laboratory parameters (neutrophils, liver and lipid parameters).

13.3 Vital signs

The summary of vital signs will only include treatment emergent data, which are defined as those vital sign measurements after the first dose of study treatment and on or before last dose + 84 days.

Analysis in vital sign measurement using descriptive summary statistics for the change from baseline for each post-baseline visit will be performed. These descriptive summaries will be presented by vital sign and treatment group. Change from baseline will only be summarized for subjects with both baseline and post-baseline values and will be calculated as:

$$\text{change from baseline} = \text{post-baseline value} - \text{baseline value}$$

The number and percentage of subjects with newly occurring notable vital signs will be presented. Criteria for notable vital sign abnormalities are provided in [Table 13-4](#):

Table 13-4 Criteria for notable vital sign abnormalities

Vital sign (unit)	Notable abnormalities
Systolic blood pressure (mmHg)	≥ 140 mmHg or < 90 mmHg
Diastolic blood pressure (mmHg)	≥ 90 mmHg or < 60 mmHg
Pulse (bpm)	> 100 bpm or < 60 bpm

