- Male sterilization (at least 6 months prior to screening). For female subjects on the study, the vasectomized male partner should be the sole partner for that subject
- Barrier methods of contraception: Condom or Occlusive cap (diaphragm or cervical/vault caps). For UK: with spermicidal foam/gel/film/cream/ vaginal suppository
- Use of oral, injected or implanted hormonal methods of contraception or other forms of hormonal contraception that have comparable efficacy (failure rate <1%), for example hormone vaginal ring or transdermal hormone contraception
- Placement of an intrauterine device or intrauterine system

In case of use of oral contraception women should have been stable on the same pill for a minimum of 3 months before taking study treatment.

Women are considered post-menopausal and not of child bearing potential if they have had 12 months of natural (spontaneous) amenorrhea with an appropriate clinical profile (e.g., age appropriate, history of vasomotor symptoms) or have had surgical bilateral oophorectomy (with or without hysterectomy) or tubal ligation at least six weeks ago. In the case of oophorectomy alone, only when the reproductive status of the woman has been confirmed by follow up hormone level assessment is she considered not of child bearing potential.

15. Active ongoing inflammatory diseases other than AS that might confound the evaluation of the benefits of secukinumab therapy, including inflammatory bowel disease or uveitis
16. Underlying metabolic, hematologic, renal, hepatic, pulmonary, neurologic, endocrine, cardiac, infectious or gastrointestinal conditions which in the opinion of the investigator immunocompromised the patient and/or places the patient at unacceptable risk in case of use of immunomodulatory therapy
17. Significant medical problems or diseases, including but not limited to the following: uncontrolled hypertension ($\geq 160/95$ mmHg), congestive heart failure (New York Heart Association status of class III or IV), uncontrolled diabetes or very poor functional status precluding ability to perform self-care
18. History of clinically significant liver disease or liver injury indicated by abnormal liver function tests, such as SGOT (AST), SGPT (ALT), alkaline phosphatase and serum bilirubin. The investigator should be guided by the following criteria:

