4.2 Treatment groups

The summaries by treatment will primarily be performed by the randomized treatment but also by combination of randomized treatment and switch treatment. For some safety summaries (e.g. exposure-adjusted) the ‘switch’ treatment may be summarized separately.

- Randomized treatment:
 - AIN457 150 mg
 - Placebo
- Treatment sequence:
 - AIN457 150 mg
 - Placebo – AIN457 150 mg
- Switch treatments (for patients who cross-over):
 - AIN457 150 mg

5 Subgroup definitions

The primary and secondary endpoints will be analyzed by region (China and non-China). Analyses by previous use of TNF- α inhibitor will also be provided for total population and Chinese population.

6 Assessment windows, baseline and post baseline definitions, missing data handling

Baseline and post-baseline definitions

In general, a *baseline* value refers to the last measurement made prior to administration of the first dose of study treatment. A post-baseline value refers to a measurement taken after the first dose of study treatment.

Analysis visit windows

Analysis visit windows will be used for the data that is summarized by visit; they are based on the study evaluation schedule and comprise a set of days around the nominal visit day. For any assessment, there are protocol defined scheduled visits around which analysis visit windows were created to cover the complete range of days within the study. The analysis visit windows and rules for dealing with multiple measurements within the windows are described in [Appendix 16.1](#).

7 Subject disposition, background and demographic characteristics

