13.4 Electrocardiogram (ECG)

The summary of ECG will only include treatment emergent data, which are defined as those ECG measurements after the first dose of study treatment and on or before last dose + 84 days.

The following quantitative variables will be summarized: ventricular rate, RR interval, PR interval, QRS duration, QT interval, and corrected QT interval (QTc). Both Bazett (QTcB) and Fridericia (QTcF) corrections will be presented for QTc.

QTc will be summarized by computing the number and percentage of subjects (including 95% confidence intervals for pooled analyses, e.g. DMC or SCS) with:

- QTc > 500 msec
- QTc > 480 msec
- QTc > 450 msec
- QTc changes from baseline > 30 msec
- QTc changes from baseline > 60 msec
- PR > 250 msec

Summary statistics will be presented for ECG variables by visit and treatment group.

In addition, shift tables comparing baseline ECG interpretation (normal, abnormal, not available, total) with the worst on-study interpretation (normal, abnormal, not available, total) will be provided.

A listing of all newly occurring or worsening abnormalities will be provided, as well as a by-subject listing of all quantitative ECG parameters.

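### The only threshold count of notable vital signs is limited to new occurrences against one high limit per pressure, so worsening from an already raised blood pressure is not counted

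*SAP*

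**What the plan says.** SAP 13.3 plans two summaries of vital signs: descriptive statistics of change from baseline by visit, and one patient count, "The number and percentage of subjects with newly occurring notable vital signs will be presented". Table 13-4 defines notable as "≥ 140 mmHg or < 90 mmHg" for systolic pressure and "≥ 90 mmHg or < 60 mmHg" for diastolic pressure. Each pressure has one high limit, with no higher tier and no category of change. Table 13-1 schedules this count as a crude incidence for Day 1 to Week 16 and for the entire treatment period.

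In SAP section 6, a baseline "value refers to the last measurement made prior to administration of the first dose of study treatment". Protocol exclusion criterion 17 removes patients with "uncontrolled hypertension ($\geq 160/95$ mmHg"). It does not remove a patient at 150/92.

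SAP 13.2 and 13.4 are worded differently. For lipids: "Summaries for newly occurring or worsening clinically notable lipid abnormalities will also be provided cumulatively". For the liver: "Newly occurring or worsening liver enzyme abnormalities will also be summarized based on the event criteria given in" a table of graded multiples of the upper limit of normal. For ECG: "A listing of all newly occurring or worsening abnormalities will be provided". Laboratory grades and ECG interpretation also have shift tables from baseline to the worst value. Vital signs have none.

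The SAP does not define a newly occurring notable value, and 13.3 does not state the denominator of its percentage.

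**The concern.** On its ordinary meaning, a newly occurring notable value is one that was absent at baseline. The explicit addition of worsening in 13.2 and 13.4 supports that reading, since it would be redundant if the shorter phrase already covered it. A patient who enters at or above 140 systolic has therefore used up the only high category for systolic pressure before the first dose. The same holds for diastolic pressure at or above 90.

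Vital signs are named in secondary objective 8. The patients left out of the high count are those nearest to clearly high values, so the table is least informative where a reader would most want a number per arm. If these patients also stay in the denominator, the reported percentage falls below the rate among patients who could be counted.

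**Working it through.** The plan gives no figure for this point, so there is none to reproduce.

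**1. The counting rule.** Define a newly occurring high as baseline below the limit and a post-baseline value at or above it, separately for each pressure. Apply this to every whole-number baseline from 140 to 159 systolic (20 values) and 90 to 94 diastolic (5 values), with rises of 0 to 80 systolic (17 steps of 5) and 0 to 50 diastolic (11 steps of 5):

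20 × 5 × 17 × 11 = 18,700 combinations, of which 0 are counted.

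| Baseline → later value | New high systolic | New high diastolic |
|---|---|---|
| 139/89 → 140/90 | counted | counted |
| 150/85 → 200/100 | not counted | counted |
| 159/94 → 200/120 | not counted | not counted |

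The gap is specific to the parameter and the direction.

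**2. How many patients start above the limit.** These inputs are assumptions: mean 118–126 / 74–80 mmHg, SD 14 / 9.5, normal distribution, entry restricted to below 160 and below 95, each pressure treated separately.

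Share = [P(≥ limit) − P(≥ entry cap)] / [1 − P(≥ entry cap)]

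- Systolic, mean 118: z = (140 − 118)/14 = 1.57 and (160 − 118)/14 = 3.00, so (0.0580 − 0.0013)/0.9987 = 5.7%.
- Systolic, mean 126: z = 1.00 and 2.43, so (0.1587 − 0.0076)/0.9924 = 15.2%.
- Diastolic, mean 74: z = (90 − 74)/9.5 = 1.68 and (95 − 74)/9.5 = 2.21, so (0.0461 − 0.0135)/0.9865 = 3.3%.
- Diastolic, mean 80: z = 1.05 and 1.58, so (0.1463 − 0.0572)/0.9428 = 9.4%.

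This gives about 6–15% for systolic and 3–9% for diastolic.

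**3. What they contribute to high readings.** Simulation: a person effect plus visit noise, within-patient correlation 0.5–0.8 (assumed), one baseline reading, and 12 on-treatment readings (the Group 1 windows in SAP Table 16-1, Week 1 to Week 52). No drug effect is included.

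- About 3–25 of 450 patients ever reach 160 systolic.
- Between about 45% and 92% of them started at 140 or more (repeat runs differ by a point or two). That is about 3–14 of 450 patients.
- Over the seven windows to Week 16, the already-high patients reaching 160 number about 2–10 of 450. One third of that, for the placebo arm of 150, is about 0.5–3.
- Patients starting at 90 diastolic or more supply about 23–65% of those ever reaching 100.
- For comparison, about 10–34% of all patients would be counted as newly at or above 140 systolic by Week 16.

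The values 160 and 100 are used here only to measure the gap. Neither is an SAP limit.

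**4. Denominator.** If a share f is already high and stays in the denominator, a true 10% among the others is shown as 10% × (1 − f). With f = 6% that is 9.4%; with f = 15% it is 8.5%.

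**The case against.** A reader might infer that a drug effect on blood pressure would be missed. The documents do not support that. On the assumptions above, about 85–94% of patients start below 140 systolic and remain countable. A general rise in pressure would show as more new values at or above 140. It would also move the change-from-baseline statistics, which include the quartiles and the maximum. The simulation contains no drug effect, so it cannot show that one would be missed. At most, an effect confined to already-high patients would go uncounted in this table.

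A reader might also infer that such a patient disappears from the report. That is too strong. SAP 16.1 says that all collected data are listed. SAP 13.1 treats an event present before the first dose as treatment-emergent if its severity increases, and Protocol 7.1 makes clinically significant abnormal test results adverse events. Worsening hypertension that the investigator judges significant can therefore be counted by patient. A patient high on one pressure can still be counted for a new high on the other, a new low, or pulse.

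The dilution in step 4 is conditional. SAP 16.2.4.1 defines crude incidence over subjects at risk, which may mean that already-notable patients leave the denominator. All that can be said is that 13.3 does not settle it.

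The comparison with other sections is also partial: the ECG wording governs a listing, not a count. The liver and lipid summaries are the sound comparison, because they are tiered patient summaries.

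These objections limit the harm. They do not remove the gap: no planned output gives the number of patients per arm whose pressure moved from raised to clearly higher.

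**Conclusion.** The point holds in a narrow form. With one high limit per pressure and a count restricted to new occurrences, a patient who enters above the limit cannot be counted as high on that parameter. Exclusion 17 allows such patients in. That conclusion follows from the text alone.

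The size rests on assumed blood pressure distributions: about 3–14 of 450 patients over 12 visits, and about 2–10 by Week 16, when the placebo comparison ends. The counts are small, but they are roughly half to nine-tenths of the patients who would ever reach 160 systolic.

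The same rule applies in both randomised arms, so this is lost sensitivity in one descriptive safety table and not bias between arms. No hypothesis test or efficacy result is affected. It is worth correcting because the correction is cheap.

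**What to change.** In Table 13-4, add a second, higher reporting tier for systolic and for diastolic pressure. The 160 and 95 mmHg figures already in the protocol would serve, for reporting only; eligibility and patient management stay as they are.

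In 13.3, count patients who newly reach each tier, and define worsening as a move from the first tier to the second. Adding the word worsening without a second tier would not be enough, because with a single limit it is undefined: a 1 mmHg rise might or might not qualify.

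State the denominator for each tier as patients not already at or above that tier at baseline. Do not assume that every patient starts below the second tier. Exclusion 17 describes uncontrolled hypertension with a paired figure, and does not guarantee that the last reading before the first dose is below 160 and below 95.

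The cost is one extra table row per pressure and an amended sentence. No new data are needed, and slightly more patients will be reported with notable values. A rise that stays within the first tier will still go uncounted, and is left to the change-from-baseline summary and the listings.

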13.4 Electrocardiogram (ECG)

The summary of ECG will only include treatment emergent data, which are defined as those ECG measurements after the first dose of study treatment and on or before last dose + 84 days.

The following quantitative variables will be summarized: ventricular rate, RR interval, PR interval, QRS duration, QT interval, and corrected QT interval (QTc). Both Bazett (QTcB) and Fridericia (QTcF) corrections will be presented for QTc.

QTc will be summarized by computing the number and percentage of subjects (including 95% confidence intervals for pooled analyses, e.g. DMC or SCS) with:

- QTc > 500 msec
- QTc > 480 msec
- QTc > 450 msec
- QTc changes from baseline > 30 msec
- QTc changes from baseline > 60 msec
- PR > 250 msec

Summary statistics will be presented for ECG variables by visit and treatment group.

In addition, shift tables comparing baseline ECG interpretation (normal, abnormal, not available, total) with the worst on-study interpretation (normal, abnormal, not available, total) will be provided.

A listing of all newly occurring or worsening abnormalities will be provided, as well as a by-subject listing of all quantitative ECG parameters.

13.6 Compound specific safety evaluation

Safety topics of interest, such as risks defined in the Safety Profiling Plan (SPP), Risk Management Plan or topics of interest regarding signal detection or routine analysis are defined in the Program Case Retrieval Sheet that is stored in CREDI at the path Cabinets/CREDI Projects/A/AIN457A/Integrated Medical Safety.

The crude incidence and exposure-adjusted incidence rates for SPP risks will be summarized. In addition, listings will be provided presenting which subjects experienced which risk.

Important note: For the evaluation of SPP risks primary and secondary system organ classes of the MedDRA dictionary will be considered.

14 Interim analyses

The primary analysis will be performed after all subjects have completed the Week 16 visit in order to support regulatory filing. As the primary analysis is scheduled at Week 16, no adjustments will be made to the testing strategy to control the family-wise type I error. The investigators, site personnel and monitors will continue to remain blinded to the treatment each subject received at randomization all patients have completed the study (Week 60 Follow up) and the final database lock has occurred. Additional analyses may be performed to support interactions with health authorities, as necessary.

15 Determination of sample size

The sample size calculation is driven by the patient exposure requirements in the study population. An overall type I error (2-sided) 5% will be used to control type I error. Secukinumab 150 mg regimen will be tested versus placebo with respect to the primary endpoint (ASAS20 response at Week 16). A sample size of 300 patients in secukinumab 150 mg group and 150 patients in placebo group (randomization ratio = 2:1) is chosen in order to expose 300 patients to secukinumab for safety evaluation and also to achieve adequate power for the primary and secondary endpoints for this study.

Analysis of an unpublished phase III study showed a placebo response rate of about 28.4% and active drug response rate of 61.1% after 16 weeks for ASAS20. Using these assumptions, overall, the power for the ASAS20 endpoint should be about 99% with 300 patients in secukinumab 150 mg group and 150 patients in placebo group based on Fisher's exact test (nQuery Advisor 7.0).

